using medications, hormonal therapy, supplements, oral contraceptives, or herbal/botanical products claimed to suppress appetite. Furthermore, exclusion criteria encompassed women with hormonal disturbances, including those in a menopausal state, and those within their menstrual cycle days or within one week prior, commonly experiencing hyperphagia due to elevated progesterone levels. Additionally, individuals with chronic diseases and metabolic disorders such as cardiovascular diseases, diabetes, hypertension, kidney diseases, thyroid disorders, gastrointestinal diseases, polycystic ovary syndrome, or androgen disorders were excluded, following a weight-reducing diet, experiencing sleep disorders, or sleeping less than 8 hours per day, and consuming less than 8 cups of water per day were also excluded from the study.

Sample size determination

The required sample size for the study was determined using the formula:

$n = 2 * (Z\alpha + Z\beta)^2 * SD^2 \div \delta^2$, where n represents the required number of participants in both the treatment and placebo groups. $Z\alpha$ and $Z\beta$ are the values from the standard normal distribution corresponding to specific confidence levels of 95% and a two-sided α of 0.05 ($Z\alpha = 1.96$) and a power of 80% ($Z\beta = 0.84$). SD refers to the standard deviation (pooled), while δ represents the estimated difference between the treatment and placebo groups.

Based on the above equation, the sample size calculation indicated that approximately 20 subjects were needed for each arm of the trial to detect a change of 1.76 μ U/mL in insulin levels between the treatment and placebo groups, with 80% power and 5% significance. The standard deviation

(SD) was assumed to be 2.1. Therefore, $n = 2 * (1.96 + 0.84)^2 * (2.1)^2 \div (1.76)^2 \approx 22$ participants per group.

To account for potential participant dropouts and to enhance the statistical power of the analysis, the number of participants was increased to 26 women per group.

Overview of the study design and procedures

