The study employed a two-arm parallel design, consisting of 52 participants who were randomized into two groups. The Greek yogurt group ($n = 26$) received one serving (380 g, 200 kcal) of zero-fat Greek yogurt, and the peanut group ($n = 26$) received one serving (35 g, 200 kcal) of unsalted peanuts. Due to one participant from each group dropping out and not attending the second visit, only 25 subjects were included in the study analysis in each group.

All participants attended two visits to the clinic. During the initial visit, participants were instructed to arrive fasting for 10-12 hours, during which anthropometry and body composition analysis were conducted. They also received education and instructions to follow a three-day low-calorie diet totaling 1200 kcal, comprising breakfast, snack 1, lunch, snack 2, and dinner, prior to the interventions. On the second visit (post-diet visit), participants received and consumed their snacks, completed the visual analog scale (VAS) questionnaire and blood samples were withdrawn.

Treatment/intervention and randomization

Intervention

Two distinct interventional snacks were provided to the participants: plain Greek yogurt and peanuts. In the Plain Greek yogurt group ($n=25$), each participant consumed 380g of plain Greek

yogurt, equating to approximately 200 calories. In the peanut group, (n=25) each participant consumed 35g of roasted, unsalted peanuts, providing approximately 200 calories.

The plain Greek yogurt (non-flavored /30g protein/13.5g carbohydrate/0g fat) was procured from the supermarket and stored in the refrigerator until serving. The peanuts (roasted, unsalted, with skin/ 8.4g protein/7.6g carbohydrate/17.5g fat) were purchased one day prior to the serving date to preserve their attributes. They were meticulously prepared in a safe and sterile manner, portioned into small transparent pouches, each containing 35g. These packed peanuts were then stored in a dry, room-temperature environment until the serving date. Table 1 shows the macro and micronutrients composition of the two interventional snacks.

The intervention was provided to each participant upon arrival at the clinic based on pre randomization and they were asked to consume it at 1:00 pm.

Randomization

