To determine differences between the means of normally distributed continuous variables in both the plain Greek yogurt and peanut groups, a Student t-test for independent samples was employed. Additionally, a paired sample t-test was used to assess variations in means of normally distributed variables before and after snack consumption in both groups. In instances where variables displayed significantly skewed distributions, medians were compared using the Mann-Whitney U test for independent samples, while paired samples were compared using the Wilcoxon Signed Rank test. A two-way repeated measures ANOVA was performed to test the main and interaction effects of Greek yogurt, peanuts, and time on appetite and insulin hormones. Additionally, the repeated measures procedure of the General Linear Model (GLM) was utilized to analyze the impact of plain Greek yogurt and peanuts on appetite perceptions over time. Correlations between gut hormones, insulin, and anthropometric measurements were assessed using the Pearson two-tailed bivariate test for continuous variables. All p-values are two-tailed, and a significance level of $p \leq 0.05$ was considered.

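### Hormone correlations have no adjustment for arm and no stated sample or time point; if the arms are pooled on post-snack values, the snack itself can create or hide a correlation

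*Combined protocol and SAP*

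**What the plan says.** The plan for correlations is one sentence in the Statistical analysis section: "Correlations between gut hormones, insulin, and anthropometric measurements were assessed using the Pearson two-tailed bivariate test". It names no covariate, no stratification by arm, no time point and no change score. The sentences before it are more specific. The independent-samples t-test names the two groups, the paired test names before and after the snack, and the repeated-measures ANOVA names both snacks and time. The section adds that "All p-values are two-tailed", with significance at p ≤ 0.05.

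Three other parts of the document bear on the point:

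- **Analysed sample.** Under the overview of design and procedures, "only 25 subjects were included in the study analysis in each group", so 50 women in all.
- **Timing.** Body composition is measured at the first visit. Blood is drawn at the second visit, once before the snack and once 60 minutes later.
- **Expected separation.** The snacks are matched at about 200 kcal but differ in composition: 30 g protein and 0 g fat for yogurt, 8.4 g protein and 17.5 g fat for peanuts. The sample size was set "to detect a change of 1.76" μU/mL in insulin between groups, with an SD of 2.1.

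**The concern.** The trial is designed to make hormones differ between arms. When two variables both shift with the assigned snack, pooling the arms puts two clouds of points at different centres, and a line through both clouds has a slope even if neither cloud has one. Randomisation does not prevent this, because the randomised snack is the common cause.

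At stake is the interpretation of hormone-hormone and hormone-insulin correlations. A pooled coefficient could be taken as a physiological link when it only repeats that both hormones responded to the snack. It could also miss a real link if the snack moves the two hormones in opposite directions. Both distortions grow as the snacks separate the hormones more.

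**Working it through.** **Inputs from the documents.** Insulin difference 1.76, SD 2.1, two-sided α 0.05, power 80%, 25 analysed per arm.

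**The plan's own figure.** 2 × (1.96 + 0.84)² × 2.1² ÷ 1.76² = 69.149 ÷ 3.0976 = 22.32, which agrees with the stated 22 per group. This calculation is for the insulin comparison; the documents give no sample size or power for the correlations.

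**Standardised difference for insulin.** d = 1.76 ÷ 2.1 = 0.838 SD. The documents give no such value for CCK, PYY, GLP-1 or ghrelin, so their differences are assumptions and are varied below.

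**Correlation induced by pooling.** With 1:1 allocation the arm indicator has variance 1/4. For two variables with unit SD within arm, within-arm correlation ρ and arm differences d1 and d2, the pooled correlation is

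r = (ρ + d1·d2/4) ÷ √[(1 + d1²/4)(1 + d2²/4)].

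For ρ = 0 and d1 = d2 = 0.838: d²/4 = 0.1756, so r = 0.1756 ÷ 1.1756 = 0.149. The pooled test is significant at |r| ≥ 0.279 (48 df).

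**False-positive rate.** Simulation of 100,000 trials per row, normal data, 25 per arm, ρ = 0, significance at p ≤ 0.05:

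| d1, d2 (SD) | r from formula | Pooled Pearson | Partial, given arm (47 df) |
|---|---|---|---|
| 0, 0 | 0 | 5.0% | 5.0% |
| 0.838, 0 | 0 | 4.9% | 5.0% |
| 0.5, 0.5 | 0.059 | 6.9% | 5.0% |
| 0.838, 0.5 | 0.094 | 9.9% | 4.9% |
| 0.838, 0.838 | 0.149 | 17.9% | 5.0% |
| 1.2, 1.2 | 0.265 | 47.7% | 5.0% |

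A Pearson test within one arm (23 df) also stays at about 5% in every row. The second row covers any pair in which one variable cannot differ systematically by arm, such as a post-snack hormone with first-visit anthropometry. Two baseline variables correspond to the first row.

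**Masking.** Take ρ = 0.4 and opposite arm effects of 0.838 SD. The pooled correlation falls to (0.4 − 0.1756) ÷ 1.1756 = 0.191. Pooled Pearson detects the association in 24.6% of simulated trials, against 82.8% for the partial correlation.

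**Price of adjusting when it is not needed.** With ρ = 0.4 and no arm effects, detection is 83.7% pooled and 82.9% partial, a loss of 0.8 percentage points.

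**The case against.** The strongest reply is that the text does not say the arms are pooled. The word bivariate rules out a covariate, but separate Pearson tests in each arm would also be bivariate, and baseline samples could have been used. Harm needs three conditions together: pooled arms, post-snack or change values, and both hormones differing by arm. This stands. A reader might infer that the plan commits to a biased analysis; the documents support only that it has no arm term and leaves the sample and time point open.

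A reader might also apply the 18% rate to all pairs. Five hormones including insulin give 10 pairs, so 10 × 17.9% is about 1.8 false positives instead of 0.5. The documents do not support that figure, because it needs all five hormones to differ by the insulin planning value and all ten pairs to be uncorrelated within arm. With insulin at 0.838 SD and the other four at 0.5 SD, still uncorrelated within arm, the expected number is 4 × 9.9% + 6 × 6.9% = 0.81. If only insulin differs, it is 0.5 and there is no inflation.

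Finally, this is a secondary analysis with no stated hypothesis. That is true and limits the importance of the point. It does not remove it, since a single sentence would settle the matter under either reading.

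**Conclusion.** The point holds conditionally. The plan uses an unadjusted Pearson correlation and does not state the sample or time point. If the 50 women are pooled on 60-minute or change values, and both hormones in a pair respond to the snack, the false-positive rate ranges from about 7% (0.5 SD each) to 48% (1.2 SD each), with 18% at 0.838 SD each. Opposite responses can instead mask a true association. These figures assume normal data, equal SDs and zero within-arm correlation (0.4 in the masking case). All arm differences other than insulin's 0.838 SD are assumed.

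Nothing here supports a wider claim. The t-tests and repeated-measures ANOVA that compare the arms are not affected.

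**What to change.** For hormone-hormone and hormone-insulin correlations on post-snack or change values, replace the bivariate test with a partial correlation controlling for arm (47 df), or report the correlation within each arm. For every correlation, state the time point and whether the arms are combined. Pairs with baseline anthropometry need no change of method on this ground.

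The partial correlation costs one degree of freedom and assumes a common within-arm correlation. Within-arm reporting avoids that assumption but has less power: the critical |r| rises from 0.282 to 0.396, and detection at ρ = 0.4 falls from about 83% to about 53% per arm. It also doubles the number of tests. Because the document already reports the analysed numbers, the change means one sentence of text and a re-run on data in hand, to be labelled as a re-analysis if the unadjusted correlations have already been run.

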At 1:00 pm, participants in the plain Greek yogurt and peanut groups consumed their assigned snacks. Following snack consumption, a validated VAS questionnaire was distributed to assess sensations and appetite levels at 0 minutes (1:00 pm), 30 minutes (1:30 pm), and 60 minutes (2:00

pm). Additionally, one hour after their arrival, at 2:00 pm, a second blood sample was collected from all participants. Throughout this period, participants were situated in a stress-free environment designed for relaxation and comfort, with soft music played to enhance their experience. No adverse events were reported by any of the participants following snack consumption.

Appetite perceptions

Appetite sensation was evaluated using a validated VAS questionnaire, designed to measure subjective ratings of hunger, fullness, satiety, prospective food consumption, and desire to eat. The VAS questionnaire included questions assessing “how strong is your feeling of” hunger, fullness, and desire to eat or “how much food can you eat right now” with anchors of “not (much) at all” to “extremely/an extreme amount”.

Participants were instructed to indicate their sensations on the scale at various time points during the study: upon arrival, 30 minutes, and 60 minutes after consuming the snack. This allowed us to discern the impact of consuming Greek yogurt and peanuts on appetite perceptions over time. The decision to assess at 30 and 60 minutes was based on the rapid increase in gut hormones following food intake, with their secretion peaking around 1-2 hours later. The VAS questionnaire was self-administered, ensuring a convenient and straightforward assessment for the participants.

Biochemical analysis

The collected blood samples (baseline and after 60 minutes of intervention) were labeled with a unique code to ensure proper identification before being transported to the medical laboratory.

The blood samples were drawn into plain tubes containing separation gel and left undisturbed until coagulation occurred. After coagulation, serum was separated from the blood cells through centrifugation at 882 $\times g$ for 20 minutes. The resulting serum was then carefully transferred into Eppendorf tubes and stored at -20 °C to preserve the integrity of the peptides for subsequent analysis. These storage procedures adhered to the recommendations outlined in studies conducted by Hallworth and Lobely.

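### No outcome is named primary, and five hormones are each tested between arms at p ≤ 0.05 with no multiplicity control and no stated deciding effect

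*Combined protocol and SAP*

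**What the plan says.** - **Threshold.** The Statistical analysis section closes with a single rule: "All p-values are two-tailed, and a significance level of" p ≤ 0.05. It gives no adjustment, no order of testing, and no label of primary, secondary or exploratory for any outcome.
- **Sample size.** The Sample size determination section looks for a difference of 1.76 μU/mL "in insulin levels between the treatment and placebo groups", with SD 2.1. It does not call insulin the primary outcome, and no other section does.
- **Hormones.** The two assay sections cover five: CCK, PYY, GLP-1 and insulin in one, ghrelin in the other. Each is measured at baseline and at 60 minutes.
- **Tests of hormones.** A two-way repeated measures ANOVA is used to "test the main and interaction effects of Greek yogurt, peanuts, and time on appetite and insulin hormones". Separately, for normally distributed variables "a Student t-test for independent samples was employed", and for skewed ones "medians were compared using the Mann-Whitney U test for independent samples". These last two sentences are not tied to particular variables or time points.
- **Appetite ratings.** The Appetite perceptions section lists "subjective ratings of hunger, fullness, satiety, prospective food consumption, and desire to eat", which is five. The sentence that begins "The VAS questionnaire included questions assessing" covers hunger, fullness, desire to eat and amount of food, with no separate satiety wording, so four may have been asked.
- **Numbers analysed.** The design overview reports that "only 25 subjects were included in the study analysis in each group".

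**The concern.** Each hormone has its own 5% chance of a false positive, and nothing in the document limits that chance across the five. Nor does it say which hormone carries the main conclusion.

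Even for one hormone the deciding result is open. The ANOVA yields a group effect and a group-by-time interaction, and these answer different questions. The group effect averages the baseline sample, taken before the snack, with the 60-minute sample. The interaction compares the change between arms. The two can disagree, and the document does not rank them.

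At stake is how the results are claimed. A conclusion that rests on whichever hormone, or whichever effect, falls below 0.05 would carry a false-positive risk well above the stated 5%.

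**Working it through.** **1. The plan's own figure.** Inputs from Sample size determination: Zα = 1.96, Zβ = 0.84, SD = 2.1, δ = 1.76.

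n = 2 × (1.96 + 0.84)² × 2.1² ÷ 1.76² = 22.32 per group. This reproduces the stated 22. The calculation spends the whole two-sided 0.05 on insulin alone.

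**2. Unadjusted error, one between-arm test per hormone at 0.05.** For k independent tests with every null true, the chance of at least one p ≤ 0.05 is 1 − 0.95^k. For an assumed equal correlation ρ between the test statistics, it is one minus the probability that k equicorrelated standard normals all lie within ±1.96. The document gives no correlations, so ρ = 0.5 and 0.8 are assumptions that show the range.

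| Hormones tested | Independent | ρ = 0.5 | ρ = 0.8 |
|---|---|---|---|
| Five, none designated | 1 − 0.95⁵ = 22.6% | 18.3% | 12.7% |
| Four, beside one recorded primary | 1 − 0.95⁴ = 18.5% | 15.6% | 11.4% |

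All entries are more than twice 5%. Paired tests and correlations, which use the same threshold, are not counted.

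**3. More than one between-arm test of the same hormone.** This was simulated for one null hormone at 25 per arm, with assumed pre-post correlation from 0.3 to 0.8. Claiming either the 60-minute t-test or the interaction gives 8.8% to 9.6%. Adding the ANOVA group effect gives 10.9% to 11.5%. These figures apply only if more than one such test is claimed.

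**4. Error under Holm, 25 per arm, t-tests (simulated).** Across five null hormones: 4.8% if independent, 4.2% at correlation 0.5, 3.0% at 0.8. With insulin tested first and Holm on the other four, all null: 4.9%.

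**5. Power under Holm.** d = 1.76 ÷ 2.1 = 0.838. With 25 per arm the noncentrality is 0.838 × √(25/2) = 2.96 on 48 degrees of freedom. The strictest Holm step is 0.05 ÷ 5 = 0.01.

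- If SD 2.1 applies to the contrast tested, power is 82.7% at 0.05 and 61.2% at 0.01.
- If SD 2.1 is the SD at a single time, d on change is 0.838 ÷ √(2(1 − r)) for pre-post correlation r, which the document does not give:

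| Assumed r | d on change | Power at 0.01 | Power at 0.05 |
|---|---|---|---|
| 0.3 | 0.708 | 43.7% | 68.9% |
| 0.5 | 0.838 | 61.2% | 82.7% |
| 0.8 | 1.325 | 97.4% | 99.6% |

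Later Holm steps are milder. If all five hormones had d = 0.838, simulated Holm power per hormone would be about 74% (independent) or 72% (correlation 0.5).

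**The case against.** **Insulin is the implied primary.** Sizing a trial on one outcome is commonly read that way, and the registration cited under Study design and participants may confirm it. If so, the insulin test keeps its 5% error. This stands as a limit: the point concerns this document only, and a reader should not infer that no primary was ever specified, or that one was changed. But sizing is not designation. The analysis section gives insulin no priority, and a confirmed insulin primary would leave the other four hormones uncontrolled.

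**The 22.6% needs every hormone to be null, and a claim resting on any one of them.** The snacks differ sharply in protein and fat, so a complete null may be doubtful, and some statisticians accept each hormone reported at its own 5%. That is a fair caution about the headline figure. The risk does not need a complete null, though: if one hormone truly differs and four do not, those four still carry the second row of the first table.

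**A reader might infer that each hormone is tested several ways, so that the error is higher still.** The document does not establish this. The t-test sentence is generic and may serve baseline characteristics, and Mann-Whitney replaces the t-test for skewed variables. What remains is that the ANOVA group effect and the interaction are not ranked.

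**A reader might also pool hormones and ratings into ten outcomes and quote 1 − 0.95¹⁰ = 40.1%** (37.0% with nine). Nothing in the document treats them as one family, and they are analysed by separately described procedures. The ratings are better seen as a second unadjusted family.

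**Conclusion.** The point holds for the five hormones. The document names no primary outcome, applies p ≤ 0.05 to each hormone without adjustment, and leaves open whether the group effect or the interaction decides. The error rates assume one test per hormone and true nulls for the hormones counted; away from independence they also rest on assumed correlations.

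Two matters are secondary: the appetite ratings as a second unadjusted family, and the rise to about 9% to 12% for a single hormone if more than one of its between-arm tests is claimed.

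The sample size formula is not at fault here, and nothing in this point touches the validity of the data. It should be corrected, and it can be corrected in the reporting.

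**What to change.** 1. **One deciding between-arm contrast for all five hormones.** Take it from an earlier dated record (registry entry or ethics submission) if one exists. Otherwise use the group-by-time interaction already in the plan, which with two time points equals the t-test on change, and Mann-Whitney on change for a skewed hormone. State that this was chosen after data collection, and state how skewness was judged; the Holm error rates above do not include that switch.
2. **If an earlier dated record names a primary outcome, whichever it is,** cite it and test it at 0.05. If it names several, share 0.05 among them by Holm. Test the remaining hormones with Holm only if the primary (all of them, if several) is significant.
3. **If no record names one,** report Holm-adjusted p-values across the five hormones beside the unadjusted ones, base the main conclusion on the adjusted values, and do not call insulin pre-specified.
4. **Appetite ratings that are not a recorded primary:** label them exploratory, or give them their own Holm family. In the second case, state that error is held at 5% within each family, not across both.

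The cost is wording and adjusted p-values, with no new data. Some hormones may lose nominal significance, by the power loss shown in step 5. With a recorded primary tested first, that outcome keeps its power at 0.05, but the remaining hormones cannot be claimed if it fails.
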